**8. Describe How Participant(s) Will Be Recruited:**

- We will advertise on UF websites ([name]'s Lab and the Department of Psychology Websites) and in local newspapers.
- Flyers and brochures will be posted in approved locations in local daycares, hospitals, clinics, birthing centers, libraries, churches, and family centers.
- [name]'s lab group will recruit by setting up informational tables and child-friendly actives (brain coloring) at local libraries, museums, and events.
- [name]'s lab will work with local community groups, including the Ounce of Prevention Fund of Florida, Florida Health Babies of Alachua County, and the Southwest Advocacy Group (Gainesville, FL), to recruit additional families from unrepresented groups. We will post fliers and brochures, have information tables at community events, and work with community group staff to identify additional recruitment avenues. We will contact these local groups and when they have a community event, we will set up a table where we hand out our brochures and flyers and ask people if they would like to be contacted to participate in our research. We will have the people who are interested fill out the BCD Lab Database Contact Permission Form, which provides their consent to put them into the database so we can contact them about our study.
- Recruitment will also occur via word of mouth and parents who participate will be asked to let their friends know about our research.
- The BCD Lab Infant Database (IRB#: IRB201601509) will be used to contact families who have already expressed interest in research participation and whose children are the appropriate age for this study.

- We will not begin recruiting or running subjects for this study until the University of Florida has reinstated in-person human research because of COVID-19. Once the university states that we are clear to begin running participants, we will continue our disinfection and cleaning after every participant comes into the lab and continue to wash our hands before and after experimentation.

**Maximum Number of Participants (to be approached with consent): 360 total, including 180 infants and 180 adult parents - 60 dyads at each age (6-, 9-, and 12-months)**

**Amount of Compensation: \$20 plus a small toy (worth \$5), \$10 after each session and the small toy is given at the end of the second session.**

**Age Range of Participants: Infants 5.5-12.5 months old, Parents 18-65 years**

**Exclusion/ Inclusion Criteria:**

- Infants will be included if they are typically developing and between 5.5 and 12.5 months of age, as well as their caregiver.
- Infants who were born more than 14 days premature are excluded.
- Infants who with a history of neurological or visual deficits are excluded.
- Infants with a history of seizures or a disorder that includes risk of seizures are excluded.
- Infants with a parent that has a history of seizures or a disorder that includes risk of seizures are excluded.
- Parents with a history of seizures or a disorder that includes risk of seizures are excluded.

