## 1. Background:

- Shared book reading during the first year of life has been found to have broad developmental benefits for language (Fletcher & Reese, 2005; Karrass & Braungart-Rieker, 2005; Sénéchal & Young, 2008), socio-emotional development (Bus et al. 1997; Xie, et al., 2018), and cognitive abilities ([name] & Monesson, 2009; 2010; [name], 2011; Pickron et al., 2018; Murray & Egan, 2014).
- Previous research suggests that infants exhibit increased attention and perceptual learning and show more specialized brain responses after parents read them books with specifically labeled (individual-level) names for faces or objects from 6- to 9-months of age (Pickron et al., 2018; [name] & Monesson, 2009; 2010; [name], 2011). However, books with generic category labels or no labels have shown no benefit to infant learning under 9 months old.
- One mechanism that may contribute to infant learning from individual-level labels during shared book reading is joint attention. Joint attention is a foundational skill that develops during the first year of life and is important for social learning and language development (e.g, Brooks & Meltzoff, 2005; Tomasello & Farrar, 1986; Mundy et al., 2007).
- The goal of the present investigation is to determine the extent to which increased parent-infant joint attention during shared book reading and across different labeling conditions leads to increases in infant visual selective attention and parent-infant neural synchrony in 6-, 9-, and 12-month-old infants.

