book) and unfamiliar characters including the following: 1) Individual-labels: familiar vs. unfamiliar; 2) Category/generic labels: familiar vs. unfamiliar; 3) No labels: familiar vs. unfamiliar

- **Day 2:** For a second EEG recording, we will measure both parent and infant EEG. This time we will be looking for EEG synchrony between the parent and infant by using a similar ssVEP frequency tagging task as above, now using a phase-locking index.
- To record brain electrical activity, a net with recording sensors is placed on the infant's head. In order to help the electrodes accurately measure the infant's brain activity, we will soak this sensor net in an electrolyte solution. The solution contains distilled water, potassium chloride (salt), and baby shampoo. Recording EEG simply picks up the brain activity that is naturally emitted from the scalp and is non-invasive. If the infant does not like wearing the net or is too tired to complete all of these tasks, the family may be asked to return to the laboratory for an additional visit.
- Outcome measures and time frame:

| Type      | Name                            | Time Frame                                      | Brief Description  |
|-----------|---------------------------------|---|--|
| Primary   | Infant Visual Fixations         | On Day 1  | Infant visual fixations will be recorded during shared book reading and duration of attention and joint attention calculated. Three age groups will be examined (6, 9, 12, month olds).                                      |
| Secondary | Parent Visual Fixations         | when their infant is 6-, 9-, 12-months on day 1 | In the lab, parent visual attention will be measured across conditions using a head mounted eye-tracker. Duration of joint attention within a spatial window will be calculated in conjunction with infant visual fixations. |
| Primary   | Infant EEG power                | On Day 2  | Infant EEG power will be measured and compared across conditions and ages.   |
| Secondary | Infant and parent EEG synchrony | On Day 2  | Infant and parent EEG synchrony will be quantified and compared across conditions.   |

- During the study, the parent will be present and near the infant at all times during each session. If the infant fusses or cries and does not wish to look at the pictures and/or read the book, we will take breaks or stop the test. If, at any point or for any reason, the participant family wishes to stop the test they may advise us to stop

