## **6. How the Sample Size is Determined:**

- Power, effect-sizes, and retention rates from [name]'s previous EEG investigations were used to estimate samples sizes. we conducted two power analyses using G\*Power (Faul, Erdfelder, Buchner, & Lang, 2009).
- First, assuming a repeated-measures ANOVA with within-subject factors of character label (individual label, generic label, control) and between-subject factors of age(6-, 9-, 12-months) and a medium effect size of  $d = 0.3$  and power of .80 each group should consist of at least 39 participants. Second, for regression analyses, the power analysis was focused on whether parent infant joint attention scores predicted infant learning (as measured by ssVEP power).
- With a medium effect size of  $f^2 = .15$  (Cohen, 1988) and power of .80, the sample should include 55 subjects.
- Given that we plan to collapse across age for this analysis, our estimated sample size of 60 per age group should be sufficient. In addition, we expect a 70% retention rate based on previous cross-sectional infant EEG investigations conducted in [name]'s laboratory and so recruiting 60 per age groups should allow for both analyses to be well powered.

---

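### Does one continuous age range of 5.5 to 12.5 months conflict with the three age groups of 6, 9 and 12 months?

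*Protocol*

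**What the plan says.** Age limits appear in one place in the Protocol, the eligibility part of Section 8. The range line reads "Age Range of Participants: Infants 5.5-12.5 months old, Parents 18-65 years", and the inclusion rule repeats it: "Infants will be included if they are typically developing and between 5.5 and 12.5 months of age".

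Everywhere else the design uses three separate ages:

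- Section 1 (Background) sets the goal in terms of "parent-infant neural synchrony in 6-, 9-, and 12-month-old infants".
- Section 3, in the outcome table, says for infant visual fixations: "Three age groups will be examined (6, 9, 12, month olds" of age.
- Section 6 (sample size) plans a repeated-measures ANOVA with "between-subject factors of age(6-, 9-, 12-months" as its levels.
- Section 8 (recruitment) sets the maximum at "60 dyads at each age (6-, 9-, and 12-months" of age, and draws on a laboratory database of families "whose children are the appropriate age for this study".

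The text available for this review gives no tolerance around 6, 9 or 12 months.

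**The concern.** Taken alone, the inclusion rule is a single band seven months wide, while the analysis factor has three points. An infant of 7.5 or 10.5 months passes the age criterion but has no defined level of the factor. If such infants were tested, someone would have to drop them or assign them to a group afterwards.

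Both outcomes would matter. Infant fixations and infant EEG power are primary outcomes, and the second aim asks whether attention differs by age. Assigning in-between infants to the nearest target would widen each group and pull the youngest and oldest groups towards each other. Dropping them would use up consented places when the margin over the required group size is small. The Background also treats 9 months as a dividing line for the effect of generic labels, so a broad 9-month group would mix infants from both sides of it.

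**Working it through.** **Inputs.** Eligible range 5.5 to 12.5 months, three target ages, and 60 dyads at each (Section 8). Required group size 39 and retention 70% (Section 6). The half-width of each group's window is not stated, so it is varied below as an assumption.

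**1. The plan's own figures.**
- 3 × 60 = 180 infants; with one parent each, 2 × 180 = 360 participants. This matches Section 8.
- Retained per group: 60 × 0.70 = 42. Section 6 states "power of .80 each group should consist of at least 39 participants", so 42 is enough. Going the other way, 39 / 0.70 = 55.7, or 56 to enrol, and 60 exceeds this.

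**2. Where the limits come from.** 6 − 0.5 = 5.5 and 12 + 0.5 = 12.5. The band ends exactly half a month outside the lowest and highest targets, as the overall range of three half-month windows would.

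**3. Share of the band outside any group.** With half-width h, the windows are 6 ± h, 9 ± h and 12 ± h, cut off at 5.5 and 12.5. Share outside = (7 − months covered) / 7.

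| h (months, assumed) | Covered | Outside | Share outside |
|---|---|---|---|
| 0.25 | 1.5 | 5.5 | 79% |
| 0.5 | 3.0 | 4.0 | 57% |
| 0.75 | 4.0 | 3.0 | 43% |
| 1.0 | 5.0 | 2.0 | 29% |
| 1.5 | 7.0 | 0.0 | 0% |

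These are shares of the calendar range, not of enrolled infants. They show how much the rule would admit if it stood alone, not whom a study recruiting to three age quotas would enrol.

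**4. Dilution if infants were assigned to the nearest target.** This needs two assumptions: recruitment spread evenly over the seven months, and cut points at 7.5 and 10.5 months. For a uniform spread, the mean is the midpoint and SD = width / √12.
- 5.5 to 7.5: mean 6.5, SD 2/√12 = 0.58.
- 7.5 to 10.5: mean 9.0, SD 3/√12 = 0.87.
- 10.5 to 12.5: mean 11.5, SD 2/√12 = 0.58.
- With one-month windows: means 6, 9 and 12, SD 1/√12 = 0.29.
- Oldest minus youngest: 11.5 − 6.5 = 5.0 months against 12 − 6 = 6.0, a reduction of 1/6 = 17%.

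The arithmetic is right, but the Protocol describes neither assumption. Nor can this figure be added to the 57%: with cut points at 7.5 and 10.5 every infant has a group, so the share outside is 0%.

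**5. Loss if in-between infants were tested and dropped.** Suppose all 180 places are filled and a share s, equal across groups, proves unclassifiable. Retained per group = 180(1 − s)/3 × 0.70 = 42(1 − s). This reaches 39 at s = 1 − 39/42 = 7.1%. The loss arises only if staff fill an age quota with infants who are not of that age.

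**The case for a change.** The strongest reply is that a quota fixes how many infants are in each group, not who counts as a 6-, 9- or 12-month-old. The database screen refers only to an appropriate age and gives no window. The inner limits that half-month windows would imply (6.5, 8.5, 9.5 and 11.5) are not written, so staff applying the eligibility rule literally could enrol a 7.5-month-old without a protocol deviation. Eligibility belongs in the protocol, so this cannot be left to a statistical analysis plan. The margin of 42 over 39 is thin.

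Much of this stands. The tolerance is unwritten in the text seen, and the eligibility section is where it would go. What does not follow is harm. The reply needs staff to apply one line of Section 8 while ignoring the age quotas in the same section and the three ages in Sections 1, 3 and 6. It also overlooks the ordinary course, which is not to schedule the infant, or to wait until the infant reaches a target age.

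The point about 9 months adds little, because any window centred on 9 months has infants on both sides of that line. The joint-attention regression in Section 6 collapses across age, so group boundaries do not affect its planned sample. Using exact age as a covariate is an analysis choice commonly left to the statistical analysis plan.

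**Conclusion.** No change to the plan is called for. The age range and the three groups are compatible: the range is the outer envelope of groups centred at 6, 9 and 12 months, and the quota of 60 dyads at each age directs recruitment to those ages. The eligibility line does omit each group's tolerance, a detail that the laboratory would fill sensibly; the outer limits point to about half a month either side, which only the sponsor can confirm. Writing it down would be tidier but would leave the 60 per group, the 180 infants and the planned ANOVA as they are.

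No bias or loss of power has been shown. The 57% depends on an assumed window and ranges from 0% to 79%. The 17% smaller contrast depends on a recruitment pattern and an assignment rule found nowhere in the Protocol. This conclusion assumes that infants are recruited at the stated ages, as the plan read as a whole directs. The part of the Protocol between Sections 6 and 8 was not available; a tolerance stated there would only strengthen the conclusion.

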## 9. Possible Discomforts and Risks:

- Only minimal risk inherent in standard clinical procedures for recording EEG in humans and using eye-tracking methods are involved in the proposed studies. All electrical equipment involved is approved for clinical research use and has been installed with attention to proper grounding. The electrode application procedures have not resulted in any known significant damage to skin. The only possible discomforts are sensitivity or allergic reaction to the saline solution (itchiness: occurs very rarely <1%), pink marks on the skin after the snug-fitting net is removed, and a small amount of conducting solution remaining in the hair until rinsed.
- Due to the length of some of the EEG and eye-tracking sessions (approximately 45 minutes to 1-hour total for infant participants), there is a risk of participant fatigue. However, we offer several breaks during each session, participants are closely monitored, and participation in any one component of the experiment takes between 5-15 minutes. If infants become consistently fussy, we will end the testing session.
- Due to the flickering nature of the stimuli there is a potential risk for individuals with Photo Sensitive Epilepsy (PSE). PSE is a form of epilepsy in which seizures are triggered by visual stimuli that form patterns in time or space, such as flashing lights, bold, regular patterns, or regular moving patterns. If anyone in the participant's immediate family has a history of seizures or PSE, this may be an applicable potential risk. To reduce the risk of seizures, we will ask all participants whether or not they have a history of PSE and we will not test those who report having such medical history.
- Psychological risks are also minimal since no pressure or stress is applied at any time. Participants will be given several breaks and are free to discontinue participation at any time.
- Confidentiality will be protected by publishing results in group form only and by storing data apart from any personal information. Data is coded according to arbitrarily assigned subject numbers and stored on password protected and encrypted computers in a locked lab. During the course of this investigation, only approved laboratory research staff have access to this data. The data files also contain information about the subject's gender, age, and race. The subject's name is recorded to ensure appropriate compensation (payment or credit), but kept separately from the data in a secured area.
- Videos of behavior and all data will be uploaded to Databrary, although de-identified, this may increase the risk of identification of individual participants. The potential risk of identification of participants will be explained to parents and parents will be given the option to exclude their video data. Data and stimuli products from this study will be made available without cost through Databrary. Databrary ([databrary.org](http://databrary.org)) funded by NSF and NICHD, is a web-based, secure

library for developmental research stimuli, videos and data. This is approved as a Data Use Agreement with the University of Florida (AGR00006970). All uploaded data will be de-identified prior to upload and participants must consent to their data being included. Study-specific code used to process and analyze the data will be available via GitHub.

De-identified eye-tracking video data of infants and parents will be available to authorized Databrary Researchers. Although data will be de-identified, images of infants and their parents may be included in the video data. Parents of participants will be informed that making the video available on Databrary increases the risk that they or their infants may be identified even though there are no names associated with any files. Parents will be informed of this risk and will have the option of excluding their videos at any time. Videos uploaded to Databrary will be viewable and downloadable to authorized users who have been granted secure access. Only researchers with Principal Investigator status from institutions with Institutional Review Boards or similar review entities, or researchers affiliated with Principal Investigators, will be authorized for access. As part of the registration process, users must agree to the conditions of use governing access to the public release data, including restrictions against attempting to identify study participants, destruction of the data after analyses are completed, reporting responsibilities, restrictions on redistribution of the data to third parties, and proper acknowledgement of the data resource. Registered users of Databrary receive user support, as well as information related to errors in the data, future releases, workshops, and publication lists.

Data in Databrary will be preserved indefinitely in a secure data storage facility at New York University (NYU). The facility is managed by the university's Information Technology Services department. Central IT staff handle storage, network, and backup systems. NYU maintains a mirror copy and does routine tape backups, both stored off site. Data and metadata stored in Databrary are subject to the security policies and best practices implemented by NYU. For more information about these policies and services, please visit NYU ITS Computer & Network Security at <http://www.nyu.edu/its/security/>. Contact PD/PI: [name]

- There are no other known or suspected risks to participants beyond the risks encountered in daily living.

#### **10. Possible Benefits:**

- There are no direct benefits to the participant.

#### **11. Conflict of Interest:**

- There are no conflicts of interest.
